## **2.2 Endpoints**

### **2.2.1 Primary Efficacy Variable:**

- Percentage change in HAM-D17

### **2.2.2 Secondary Efficacy Variables:**

- Percentage change in HAM-D6
- Percentage change in QIDS-SR16
- Percentage change in PHQ-9
- Responders of HAM-D17, HAM-D6, QIDS-SR16, and PHQ-9
- Remitters of HAM-D17, HAM-D6, QIDS-SR16, and PHQ-9

### **2.2.3 Exploratory, Safety, and Tolerability Variables**

- Percentage change in GAD-7
- Percentage change in CGI-S
- Change in SF-36
- Responders of GAD-7, CGI-S, CGI-I, CGI-EI, and SF-36
- Remitters of GAD-7, and CGI-S
- Change in EuroQol (EQ-5D-5L)
- Change in BARS
- Percentage of patients on congruent medications
- Prescription filling frequency between study visits
- Number of Adverse Events (AE)
- Change in UKU

- Change in FIBSER

### **3 GENERAL CONSIDERATIONS**

#### **3.1 Timing of Analyses**

A definitive statistical analysis of the primary and 8-week secondary outcome measure will be performed by the trial statistician when all of the following have been achieved:

- All subjects recruited into the study have been followed up for 8 weeks or have been deemed to be lost to follow-up;
- All CRFs have been entered onto the computer database;
- All data have been checked for completeness, and the accuracy of all data entries have been verified; and
- Evaluability status of subjects has been determined;

Long-term and secondary outcome measures of efficacy and safety will be performed by the trial statistician when all of the following have been achieved:

- All subjects recruited into the study have been followed up for 12 months or have been deemed to be lost to follow-up;
- All CRFs have been entered onto the computer database;
- All data have been checked for completeness, and the accuracy of all data entries have been verified;
- Evaluability status of subjects has been determined; and
- Database has been locked.

#### **3.2 Analysis Populations**

##### **3.2.1 Per Protocol (PP) Population**

The primary statistical analysis will be performed using the Per Protocol (PP) principle. The population of this analysis will be all subjects who met the inclusion and exclusion criteria. Other variables relating to exclusion may include but are not limited to:

At screening:

- a) Meets all inclusion/exclusion criteria (except exception 8 and 13)
- b) All assessments completed by appropriate person
- c) QIDS-C16 and -SR16 are  $\geq 11$

At baseline:

- a) Confirmation that subject still satisfies all Inclusion/Exclusion criteria
- b) Randomization occurred prior to the Baseline visit

- c) All assessments completed by appropriate person. The Blinded Rater should administer the QIDS-C16, not the Treating Clinician.
- d) Baseline was completed within 42 days of screening
- e) Sample was received and report was released (GEN & E-GEN) prior to baseline
- f) Report was viewed (GEN & E-GEN) at/prior to baseline
  - o If report not viewed at/prior to baseline, prescription decision date must follow view date of report
- g) Baseline QIDS-SR is  $\geq 11$
- h) Baseline HAM-D-17  $\geq 14$

After enrollment:

- a) Week 4 visit occurs within 20-36 days of baseline visit
- b) Week 8 visit occurs within 48-64 days of baseline visit
- c) QIDS-C16 completed by Blinded Rater, not Treating Clinician
- d) Subject did not start ECT, DBS, or TMS
- e) MDD Rx given by study affiliated clinician
- f) If unblinding occurs before week 8 visit, data is not included in PP population

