If at the end of the screening period the participant is found to be ineligible as per the inclusion/exclusion criteria, then the participant will become a Screen Failure and is exited from the study. The UPI will not be reused. If the participant is eligible at the end of the screening period, then the participant will be enrolled and randomized. If the participant is found to be ineligible as per the inclusion/exclusion criteria at baseline, then the subject will become a Randomization Failure.

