13.0 BLINDING

This study will be conducted under double-blind conditions so that neither the patient nor study staff members involved in patient assessments will know whether the patient is receiving GEN, E-GEN, or TAU. Only the treating clinician at the study site and AssureRx will have knowledge of the intervention arm assigned to the patient.

All assessments will be administered by the site, with the exception of the primary outcome measure (HAM-D₁₇), which will be conducted by 1-2 trained central rater(s) not involved in the clinical care of the individual and blinded to the treatment allocation. The rater will be trained and inter-rater reliability will be determined through rater scoring of the HAM-D₁₇ while viewing a DVD-recording of a standardized patient interview.

At randomization, the treating clinician will receive the results of the GEN test for patients allocated to GEN and the results of the E-GEN test for patients allocated to the E-GEN, and may decide to change the participant's treatment based on the results of the test. The treating clinician will therefore not be blinded to treatment allocation. AssureRx will also not be blinded to treatment allocation in order to release the appropriate report (either GEN, E-GEN or no report (TAU)) to the treating clinician and to provide follow-up support to the treating clinician on report interpretation. However, both treating clinician and AssureRx will be blinded to trial data.

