16.0 STATISTICAL METHODS

16.1 Clinical Analysis

Hall-Flavin et al.(11) experienced significant participant attrition during the course of their investigation. Post hoc analyses using intention-to-treat (ITT) analyses, however, revealed little differences between the observed data and imputed data (e.g., last observation carried forward (LOCF) and estimation/maximization (EM) algorithm imputation). Two analyses will be completed with the study data: under the principle of intention-to-treat all randomized individuals will be analysed, i.e., the Full Analysis Set (FES), and a per protocol (PP) analysis for randomized participants where adherence to the protocol and visits was followed. Therefore, to account for participant attrition in the current study, ITT with multiple imputation with LOCF and EM algorithm imputation will be employed to account for missing data, assuming the data are missing completely at random. To assess the potential impact that the multiple imputation has on the final estimates, an EM algorithm imputation (iterative mean imputation) will be used as exploratory sensitivity analysis.

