## **1.2 Objective of the Analyses**

The analyses detailed in this document will assess the efficacy and safety of the patients treated with GeneSight guidance in comparison with the patients treated without GeneSight guidance. This analysis plan supersedes the one in the protocol and the previous versions.

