### **3.2.2 Intention to Treat (ITT) Population**

The population for this analysis will be all subjects who met the inclusion and exclusion criteria at screening, and were randomized. Subjects that meet inclusion and exclusion criteria and were randomized but have low baseline QIDS-SR scores will be included in ITT analysis.

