### **3.4 Missing Data**

Missing observations of response variables will be checked and missing patterns by treatment and overall will be described including a CONSORT trial flow diagram. Missing values will be handled by using maximum likelihood method (ML). Complete cases analyses will be conducted and results will be compared to those obtained from ML. The main analysis conclusion at Week 8 will be drawn using ML method for the PP population (see Section 5.1).

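### The SAP lets a per-protocol set, filtered after randomisation and partly by criteria only the report arms can fail, decide GEN versus TAU; the planned ITT model should decide it

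*SAP*

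**What the plan says.** - **Which plan governs.** SAP 1.2: "This analysis plan supersedes the one in the protocol and the previous versions".
- **Which set decides.** SAP 3.2.1: "The primary statistical analysis will be performed using the Per Protocol (PP) principle". SAP 3.4: "The main analysis conclusion at Week 8 will be drawn using ML method for the PP population". The hypothesis in SAP 2.1.1 is a difference between GEN and TAU in percentage change in HAM-D17 at Week 8, not non-inferiority.
- **What the protocol had planned.** Section 16.1: "under the principle of intention-to-treat all randomized individuals will be analysed", with a PP analysis beside it.
- **When the PP filters act.** Protocol 9.1 randomises eligible patients at the end of screening. Baseline item b of the PP list itself requires randomisation before the baseline visit.
- **What the PP filters are.** Baseline items e and f, both marked for GEN and E-GEN, concern release and viewing of the report. If the report was not viewed by baseline, f is still met when the prescribing decision follows the viewing. Other items include a re-check of all eligibility criteria at baseline, score thresholds (g, h), visit windows, start of ECT, DBS or TMS, who prescribed, and unblinding before Week 8. The list is introduced as not exhaustive.
- **What is planned for ITT.** SAP 5.1 repeats the mixed model (MMRM) and the complete-case analysis on the ITT set, and SAP 4 promises separate PP and ITT tables. SAP 3.2.2 defines ITT as "all subjects who met the inclusion and exclusion criteria at screening, and were randomized". In SAP 5.2, ITT is optional for secondary analyses.

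**The concern.** In a superiority comparison, randomisation justifies the inference only if the sets compared are those that randomisation created. Here the deciding set is selected afterwards, and one part of the selection can act on one side only. PP compares GEN patients whose report was released, and viewed before prescribing, with TAU patients who faced no such test. That is not the effect of offering the test, which is what the real-world comparison in Protocol 3.5 and the health technology application in SAP 1.1 call for. If PP and ITT disagree, SAP 3.4 lets PP decide.

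**Working it through.** **1. Which criteria can act on one arm only.**

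| PP item (SAP 3.2.1) | Can it exclude a TAU patient? | Basis |
|---|---|---|
| Baseline e, sample received | Possibly | DNA is also collected in TAU (Protocol 7.1.3) |
| Baseline e, report released | No | TAU clinicians get no report until at most 28 days before the 12-month completion (Protocol 7.1.3) |
| Baseline f, report viewed, or prescribing after viewing | No | As above |
| Baseline g and h, QIDS-SR ≥ 11 and HAM-D17 ≥ 14 | Yes, alike in all arms | Not part of the concern |

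Item f also depends on what the clinician did, and Protocol 13.0 says: "The treating clinician will therefore not be blinded to treatment allocation".

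**2. Other post-randomisation items.** Exclusion 13 (psychotropic change between screening and baseline) is excepted at screening but falls under the re-check of all criteria at baseline. By then the GEN clinician may hold the report: "At randomization, the treating clinician will receive the results of the GEN test" (Protocol 13.0). Starting ECT, DBS or TMS, prescriber affiliation and unblinding could likewise depend on arm or outcome. Nothing in the documents shows that they do.

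**3. Size of the effect of e and f.** The plan gives no exclusion rate and no link between exclusion and prognosis, so it has no figure to reproduce on this point. The illustration uses:

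- n per arm = 190 × (1 − 0.167) = 158 (Protocol 10.0).
- q = share of GEN removed by e and f (assumed).
- δ = mean improvement of kept minus excluded GEN patients, in SD (assumed).

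If all GEN patients together equal TAU, the kept mean k satisfies (1 − q)k + q(k − δ) = TAU mean, so bias = k − TAU mean = qδ. Then ncp = qδ / √(1/158 + 1/(158(1 − q))), and two-sided rejection = P(Z > 1.96 − ncp) + P(Z < −1.96 − ncp).

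| q | GEN kept | Bias, δ = 0.3 to 0.5 (SD) | ncp | Two-sided type I error |
|---|---|---|---|---|
| 2% | 155 | 0.006 to 0.010 | 0.053 to 0.088 | 5.0 to 5.1% |
| 5% | 150 | 0.015 to 0.025 | 0.132 to 0.219 | 5.2 to 5.6% |
| 10% | 142 | 0.03 to 0.05 | 0.260 to 0.433 | 5.8 to 7.2% |

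A bias of 0.05 SD is 0.05/0.30 = 17% of the planned effect. With δ = 0 the error stays at 5.0%. If the excluded would have done better (δ = −0.3 to −0.5, q = 10%), the chance of a false GEN advantage falls from 2.5% to 1.3 to 0.8%, and a real benefit is understated. That chance doubles to 5% only at q of about 12% (δ = 0.3) or 7% (δ = 0.5).

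**4. What ITT costs in power.** Suppose a share q of GEN gets no benefit because the report was not viewed before prescribing (assumed). The ITT effect is 0.30(1 − q), and power = P(Z > 1.96 − effect/√(2/158)). PP keeps 0.30 with 158 against 158(1 − q).

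| q | ITT effect (SD) | ITT power | PP power |
|---|---|---|---|
| 0 | 0.30 | 76% | 76% |
| 5% | 0.285 | 72% | 75% |
| 10% | 0.27 | 67% | 74% |

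This is a two-sample approximation without the baseline covariate, for comparing sets only. Its distance from the protocol's stated 90% is a separate question.

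**The case against.** The strongest defence is that little may be at stake. Reports come back within three days of sample receipt (Protocol 7.1.1), baseline may follow screening by up to 14 days (Protocol 9.3; PP allows 42), and f has a fallback, so e and f may seldom exclude anyone. The ITT model and separate tables would expose a divergence. All of that stands. It limits the likely size, but it does not change which result decides.

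Several stronger readings are tempting, and the documents do not support them:

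- *A reader might infer that PP favours GEN.* The direction is unknown; it could favour TAU.
- *That PP keeps only patients whose clinician followed the report.* Item f concerns viewing. Following the report is congruence (SAP 7.4), which is not a PP criterion.
- *That medication changes before baseline will differ by arm.* Protocol 9.1 says psychotropic medication should not be modified in that period in any arm, benzodiazepines excepted.
- *That evaluability will be decided with outcomes in view.* SAP 3.1 does not say who decides, but Protocol 13.0 keeps the treating clinician and the laboratory blind to trial data.
- *That the SAP's ITT set drops patients found ineligible at baseline.* Of such a patient Protocol 9.1 says "then the subject will become a Randomization Failure". Read literally, though, SAP 3.2.2 keeps anyone who passed screening and was randomised, so it differs from all randomised mainly for randomisation errors.
- *That e and f distort GEN versus E-GEN.* They apply equally to both arms.

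**Conclusion.** The point holds as a matter of design. A superiority conclusion rests on a set formed after randomisation, with report release and viewing able to exclude only report-arm patients and with an open list of further exclusions. This follows from the text and needs no assumption.

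The size is not established. The 0.015 to 0.05 SD bias and 5.2 to 7.2% type I error hold only for the assumed 5 to 10% exclusion and 0.3 to 0.5 SD deficit; the true bias may be zero or of opposite sign. The other post-randomisation items are not quantified. The case for change is that the plan does not bound the bias and the remedy is cheap, not that a large error has been shown.

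**What to change.** 1. In SAP 3.2, 3.4 and 5.1, make ITT the primary population and draw the main Week 8 conclusion from the ITT MMRM already planned.
2. Word SAP 3.2.2 to match Protocol 16.1 (all randomised). Confirm in one sentence that patients found ineligible at baseline after randomisation stay in. Those with no baseline or no post-baseline HAM-D17 still add nothing to the model.
3. Keep PP as supportive, with a closed list and with membership fixed before unblinding and blind to outcome. Items e and f reveal the arm, so whoever applies them should have no outcome data.
4. In SAP 5.2 make the ITT analysis mandatory. In SAP 2.1.2.2 state that ITT governs the choice of groups for later comparisons. The SAP does not now say which set governs there; that gap, not the arm asymmetry, is the reason.
5. Add an ITT sensitivity analysis restricted by baseline thresholds g and h.

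**Cost.** SAP wording and one sensitivity analysis; sample size and alpha do not change. There are two downsides. First, the effect may be diluted, as shown in the power comparison; that dilution is part of the effect of offering the test. Second, ITT keeps patients with low baseline HAM-D17 (the inclusion criteria set no HAM-D17 floor), for whom percentage change can be extreme: a 7-point change is 7/14 = 50% from a baseline of 14 but 7/7 = 100% from a baseline of 7. The Huber weighting in SAP 5.1 covers only the complete-case analysis, hence step 5.

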6.2.1 Inclusion Criteria

1. 18 years of age or older;
2. Suffer from a Major Depressive Episode meeting Diagnostic and Statistical Manual of Mental Disorders, Fourth Edition, Text Revision (DSM-IV-TR) criteria;
3. Have had an inadequate response within the current episode to at least one psychotropic treatment (listed in Appendix I). Inadequate response is defined as inadequate efficacy after 6 weeks of a psychotropic treatment or discontinuation of a psychotropic treatment due to adverse events (AEs) or intolerability;
4. Have each a screening and baseline score on the 16-item Clinician Quick Inventory of Depressive Symptomatology (QIDS-C₁₆) and 16-item Self-Report Quick Inventory of Depressive Symptomatology (QIDS-SR₁₆) rating scales ≥ 11 ;
5. Be able to understand the requirements of the study and provide written informed consent to participate in this study;
6. Agree to abide by the study protocol and its restrictions and be able to complete all aspects of the study, including all visits and tests.

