6.2.2 Exclusion Criteria

Any of the following conditions are cause for exclusion from the study:

1. Patients posing a serious suicidal risk and/or in need of immediate hospitalization as judged by the Investigator;
2. Patients with a diagnosis of Bipolar I or II disorder;
3. Patients with a current Axis I diagnosis of:
 - Delirium
 - Dementia
 - Amnestic and/or other cognitive disorder
 - Schizophrenia or other psychotic disorder;
4. Patients having experienced hallucinations, delusions, or any psychotic symptomatology within the current depressive episode or during prior depressive episodes;
5. Patient is currently in an inpatient facility;
6. Patients with a history of hypothyroidism unless taking a stable dose of thyroid medication and asymptomatic or euthyroid for at least 6 months;

7. Patients who meet DSM-IV-TR criteria for any significant current substance use disorder;
8. Patients with:
 - hepatic insufficiency (three times the upper limit of normal (ULN) for aspartate aminotransferase (AST) and/or alanine aminotransferase (ALT)); liver transplant recipient; cirrhosis of the liver;
 - malignancy (except basal cell carcinoma) and/or chemotherapy within 1 year prior to screening; malignancy more than 1 year prior to screening must have been local and without metastasis and/or recurrence, and if treated with chemotherapy, without nervous system complications;
 - significant unstable medical condition or life threatening disease with anticipated survival of less than 6 months;
 - need for therapies that may obscure the results of treatment and/or of the study;
9. Participation in another clinical trial within 30 days of the screening visit;
10. Anticipated inability to attend scheduled study visits;
11. Patients who in the judgment of the Investigator may be unreliable or uncooperative with the evaluation procedure outlined in this protocol;
12. Patients with a history of prior pharmacogenomic testing;
13. Any change in psychotropic medication (including change in dosage) between screening and baseline;
14. Patients currently receiving electroconvulsive therapy (ECT), deep brain stimulation (DBS) or transcranial magnetic stimulation (TMS) treatments, or currently scheduled to receive maintenance treatments of ECT, DBS, or TMS during the course of the study;
15. Patients who self-report to be pregnant or lactating;
16. Patients with a history of gastric bypass surgery

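### The primary per-protocol set has no Week 8 limit on its ECT/DBS/TMS and outside-prescriber rules, and adds a baseline HAM-D17 floor that the protocol never used for entry

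*SAP*

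**What the plan says.** SAP 3.2.1 makes PP the primary set: "The primary statistical analysis will be performed using the Per Protocol (PP) principle". SAP 3.4 draws the main Week 8 conclusion from it. The set starts from patients who satisfied the entry criteria, then gives a list introduced by "Other variables relating to exclusion may include but are not limited to". Four items matter here.

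- Baseline item (h): "Baseline HAM-D-17" of at least 14.
- After-enrollment item (d): "Subject did not start ECT, DBS, or TMS", with no end date.
- After-enrollment item (e): depression prescriptions must come from a clinician affiliated with the study, also with no end date.
- After-enrollment item (f): "If unblinding occurs before week 8 visit, data is not included in PP population".

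The protocol sets severity at entry by the QIDS alone: "Have each a screening and baseline score on the 16-item Clinician Quick Inventory of Depressive Symptomatology", together with the self-report version, on "rating scales ≥ 11" (Protocol 6.2.1, item 4). No inclusion or exclusion criterion mentions HAM-D17. ECT, DBS and TMS appear only as an entry exclusion, for patients receiving them at the time "or currently scheduled to receive maintenance treatments of ECT, DBS, or TMS during the course of the study" (Protocol 6.2.2, item 14). Starting one later is not named among the withdrawal scenarios in Protocol 14.1.2, although investigator judgement is. Protocol 16.1 describes PP as randomised participants who adhered to the protocol and its visits.

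**The concern.** Because PP carries the headline result, any exclusion in it that is not a matter of adherence changes what the trial reports. The two rules differ in kind.

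Items (d) and (e) concern events after randomisation. If they apply beyond a patient's own Week 8 visit, they select on something that follows the outcome and could plausibly result from it. The treating clinician knows the arm (Protocol 13.0), so selection could differ between arms.

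Item (h) uses a baseline score. A patient can meet every entry criterion, attend every visit, follow the protocol throughout, and still leave the primary analysis. The question answered is then about a narrower population than the one recruited. The sample size allowed only for premature discontinuation, so these losses come on top.

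**Working it through.** **Items (d) and (e): reading the text**

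1. Under the after-enrollment heading, (a) and (b) give Week 4 and Week 8 visit windows and (f) stops at the Week 8 visit. Items (d) and (e) carry no time limit.
2. The Week 8 analysis waits until every patient has reached Week 8 or is lost, and until evaluability has been determined (SAP 3.1). Planned recruitment is 24 months (Protocol 11.0). The last Week 8 visit therefore falls at about 24 months + 8 weeks, or roughly month 26.
3. Patients enrolled up to about month 26 − 12 = 14 would by then have completed 12 months of follow-up. That is about 12 months − 8 weeks, or roughly 10 months beyond their own Week 8. The last patient enrolled has almost none.
4. On the literal wording, a start in that interval removes a Week 8 score already validly recorded, and early enrollees are exposed to the rule for longer.
5. SAP 5.2 uses the PP population for the secondary analyses too, and those include visits after Week 8. An unlimited reading of (d) is therefore realistic.

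**Item (h): loss of numbers**

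Inputs from Protocol 10.0: 190 per arm, effect size 0.30, alpha 0.05, power 90%, 16.7% premature discontinuation. The test is two-sided (SAP 6).

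1. The plan's own figure. Two-sided pairwise n per arm = 2 × (1.960 + 1.282)² / 0.30² = 233.5, so 234. After discontinuation this is 234 / 0.833 = 281 per arm, not 190. The stated 570 is not reproduced, and the protocol does not describe how its 20% intraclass coefficient entered. That is a separate issue. The planned 190 is used here only as the starting point.
2. Left at Week 8: 190 × (1 − 0.167) = 158 per arm.
3. Pairwise power = Φ(0.30 × √(n/2) − 1.960). At n = 158: Φ(2.666 − 1.960) = 76.0%.
4. The documents give no baseline HAM-D17 distribution. Assume a normal distribution with mean 18 to 20 and SD 4 to 5. With continuity correction, the share below 14 is Φ((13.5 − mean)/SD).

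| Assumed mean, SD | Share below 14 | n per arm | Power |
|---|---|---|---|
| 20, 4 | Φ(−1.625) = 5.2% | 150 | Φ(2.598 − 1.960) = 74% |
| 18, 4 | Φ(−1.125) = 13.0% | 137 | 70% |
| 19, 5 | Φ(−1.100) = 13.6% | 137 | 70% |
| 18, 5 | Φ(−0.900) = 18.4% | 129 | Φ(2.409 − 1.960) = 67% |

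These powers ignore clustering, treat the 16.7% as fully lost, and hold the effect size at 0.30.

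**The case against.** Several points on the other side have weight.

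- The missing limit is silence, not an instruction. Every dated after-enrollment item ends at or before Week 8, and so does the main conclusion. A limit at Week 8 is a natural reading of (d) and (e). This stands as a reading, but the wording does not secure it.
- The list is permissive, so it is too strong to say that the SAP deletes these patients. The open wording also leaves membership more to discretion, which is no comfort in a primary set.
- A floor on HAM-D17 has an endpoint rationale. The outcome is a percentage change, so a low baseline gives an unstable ratio. The score comes from a blinded central rater before any medication change (Protocol 9.3, 13.0), and the same cut applies in all arms. This stands: (h) is chiefly a matter of population and numbers, not of bias.
- The SAP supersedes the protocol's analysis plan (SAP 1.2), repeats the primary analyses in ITT (SAP 5.1) and tabulates both sets. The ITT definition (SAP 3.2.2) has no HAM-D17 or ECT condition, so the effect of these rules will be visible.
- The power loss may be overstated. The mixed model uses Week 4 data from later dropouts, and removing unstable percentages could reduce the SD.

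A reader might also infer that the primary result would change when the data are run again at 12 months. The documents do not support that. SAP 3.1 plans one definitive Week 8 analysis after evaluability is determined, and the later run covers long-term and secondary outcomes.

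**Conclusion.** The point holds as a recommended change to the wording of the primary analysis set.

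Items (d) and (e) lack the limit that (f) has. Read literally, they can remove valid Week 8 scores because of later events. The exposure is confined to starts between a patient's own Week 8 visit and the determination of evaluability. A reader might infer a bias against or in favour of the test. Neither can be supported: the documents give no rates of starting these treatments by arm or by response, and the direction changes with the rates assumed.

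Item (h) lies outside the protocol's entry criteria and its description of PP, and the SAP gives no reason for it. If 5% to 18% of patients score below 14, the set falls from about 158 to between 150 and 129 per arm, and power from about 76% to between 74% and 67%. The lower end depends wholly on the assumed baseline distribution.

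The ITT repeat mitigates both points. It does not settle them, because the main conclusion is tied to PP.

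**What to change.** 1. For the Week 8 analysis, add *before the Week 8 visit* to after-enrollment items (d) and (e), matching (f).
2. Remove (h) from the primary PP set. If the sponsor prefers to keep the floor, at least repeat the primary mixed model on the PP set without (h).
3. In either case, present baseline HAM-D17 of at least 14 versus below 14 as a pre-specified subgroup.

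The cost is SAP wording and, at most, one extra model and one table. No new data are needed. The downside of removing (h) is that a few low-baseline patients with unstable percentage change enter the primary set. The subgroup display would show how much they matter.

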9.0 STUDY TIME SCHEDULE

Study evaluation measures will be obtained over a 1-year period and will consist of seven scheduled assessments, not including screening and enrollment (Figure 1). Assessment visits will occur at baseline, 4 weeks, 8 weeks, 12 weeks, 6 months, 9 months and 12 months following randomization. The short-term follow-up visits will occur up to and including 12 weeks with the assessment of the primary outcome at 8 weeks, followed by long-term study visits at 6, 9 and 12 months. The following outlines the evaluations to be completed at each of the visits.

Figure 1. Study Time Schedule

Time Point	STUDY PERIOD								Early Termination Visit (ET)
	Screening/ Randomization - t1 (Visit 1)	Baseline t0 (Visit 2)	Short-term visits			Long-term follow-up			
			Week 4 (Visit 3)	Week 8 (Visit 4)	Week 12 (Visit 5)	Month 6 (Visit 6)	Month 9 (Visit 7)	Month 12 (Visit 8)	
ENROLLMENT									
Informed consent	x								
Eligibility screening	x								
Randomization	x								
Eligibility baseline		x							
INTERVENTIONS									
GeneSight Psychotropic (GEN)			_____	_____	_____	_____	_____	_____	
Enhanced GeneSight Psychotropic (E-GEN)			_____	_____	_____	_____	_____	_____	
Treatment as usual (TAU)			_____	_____	_____	_____	_____	_____	
ASSESSMENTS									
Buccal swab for genotyping	x								
Vital signs	x								
Mini International Neuropsychiatric Interview (MINI) for Axis 1	x								
Diagnostic and Statistical Manual of Mental Disorders, Fourth Edition, Text Revision (DSM-IV-TR) criteria for MDD	x								
DSM-IV-TR criteria for current substance use disorder	x								
Phlebotomy for laboratory panel	x								
Biobank sample	x								
Urine sample for drug screen and laboratory panel	x								
16-item Clinician Quick Inventory of Depressive Symptomatology (QIDS-C ₁₆)	x								
16-item Self Report Quick Inventory of Depressive Symptomatology (QIDS-SR ₁₆)	x	x	x	x	x			x	x
Changes to initial prescribing based on availability of pharmacogenomic data	x	x							
Medical history and psychiatric history	x	x							
Psychotropic medication history (current and past) and response	x	x							
Past (within one month) concomitant non-psychotropic medications	x	x							
Current concomitant non-psychotropic medications	x	x	x	x	x	x	x	x	x
Demographics, Employment, Insurance		x							
Smoking status and amounts		x	x	x	x			x	x
Height		x							
Weight and waist-to-hip ratio		x	x	x	x			x	x
Adverse events (AEs)		x	x	x	x			x	x

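### After enrollment, the rater check for the primary (per-protocol) set names the QIDS-C16, which is not scheduled at Week 4 or Week 8, and no item expressly checks who rated the HAM-D17 at those visits

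*SAP*

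**What the plan says.** SAP 3.2.1 makes the PP set the basis of the primary analysis and lists conditions at screening, at baseline and after enrollment. The list is introduced with "Other variables relating to exclusion may include but are not limited to".

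Four of its items bear on raters or blinding:

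- Screening (b) and the first sentence of baseline (c): "All assessments completed by appropriate person".
- The second sentence of baseline (c): "The Blinded Rater should administer the QIDS-C16, not the Treating Clinician".
- After-enrollment (c): "QIDS-C16 completed by Blinded Rater, not Treating Clinician".
- After-enrollment (f): "If unblinding occurs before week 8 visit, data is not included in PP population".

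The primary endpoint (SAP 5.1) is percentage change in HAM-D17 to Week 8, from a repeated-measures model of Weeks 4 and 8. Protocol section 13 assigns the HAM-D17 to central raters, "which will be conducted by 1-2 trained central rater(s) not involved in the clinical care" and blinded to allocation, and leaves every other assessment to the site. It also states that the treating clinician knows the allocation.

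**The concern.** A PP rule on raters exists so that an outcome scored by someone who knows the arm does not enter the primary analysis. Here the treating clinician is unblinded by design and the outcome is an interviewer-rated scale, so the identity of the rater matters for bias.

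After baseline, the rule is attached to a different instrument. If that instrument is not collected at those visits, the rule has no data to act on and the outcome it should protect goes unchecked. The SAP also leaves open what a missing QIDS-C16 does to a subject's PP status. That decision would then be taken when evaluability is determined, which SAP 3.1 requires before the 8-week analysis.

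**Working it through.** This is a cross-check of documents. No sample size, power or alpha figure is involved.

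**Step 1. Set the schedule beside the PP rater items.** Sources are protocol Figure 1, sections 6.2.1, 9.1 and 9.3 to 9.5, and SAP 3.2.1.

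| Visit | QIDS-C16 scheduled? | HAM-D17 rater in protocol | PP item on the rater |
|---|---|---|---|
| Screening | Yes (Figure 1, 9.1) | HAM-D17 not given | General sentence, screening (b) |
| Baseline | Not in Figure 1 or 9.3, but required by inclusion criterion 4 | Central rater (9.3) | General sentence in (c), plus the QIDS-C16 sentence |
| Week 4 | No (Figure 1, 9.4) | Central rater (9.4) | After-enrollment (c), QIDS-C16 only |
| Week 8 | No (Figure 1; 9.5 repeats Week 4) | Central rater (9.5, by reference to 9.4) | After-enrollment (c), QIDS-C16 only |

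Figure 1 marks the QIDS-C16 once, among rows marked only at screening. The visit lists agree for Weeks 4 and 8, so the gap does not hang on how one table row is read.

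**Step 2. Apply after-enrollment (c) as written.** With no scheduled QIDS-C16 at Week 4 or Week 8, there are two readings:

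- As a requirement that a QIDS-C16 by the blinded rater exists, no participant following the schedule meets it.
- As a condition on who rates a QIDS-C16 if one is done, no participant following the schedule fails it.

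Under either reading the item treats every such participant alike. It cannot separate a HAM-D17 scored by the central rater from one scored by someone else. Even a stray QIDS-C16 would not help, because section 13 gives that scale to the site and only the HAM-D17 to the central rater.

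**Step 3. Count what is left unchecked.** The primary analysis uses three HAM-D17 assessments per participant. Baseline is the denominator and covariate, and Weeks 4 and 8 are the modelled responses. The rater is covered at 1 of the 3 and not expressly checked at 2 of the 3, which are both of the responses. For GEN against TAU at the planned 190 per arm, that is 190 × 2 arms × 2 visits = 760 ratings before dropout. This is the number without an explicit check. It is not a count of wrong ratings, for which the documents give no rate.

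**Step 4. Look at baseline separately.** Inclusion criterion 4 reads "Have each a screening and baseline score on the 16-item Clinician Quick Inventory of Depressive Symptomatology" (and the self-report version) of at least 11, and PP baseline (a) re-checks all criteria. Figure 1 and section 9.3 list no baseline QIDS-C16. PP baseline (g) sets a threshold only for the QIDS-SR, and SAP 3.2.2 mentions only low baseline QIDS-SR scores. The documents therefore disagree on whether a baseline QIDS-C16 exists. Weeks 4 and 8 carry no such disagreement.

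**The case against.** The strongest case is that the HAM-D17 is already protected.

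- **The PP rules do cover the HAM-D17.** A reader might infer from item (c) that its rater is never checked. That is not so: the general sentence in baseline (c) takes in every baseline assessment, and baseline (h) sets a HAM-D17 threshold. This point stands and confines the gap to Weeks 4 and 8. The general sentence is not repeated after enrollment.
- **Unblinding before Week 8 removes the data.** This helps in part. But the treating clinician knows the arm by design, so a HAM-D17 scored by that clinician need not be logged as unblinding, and an event at the Week 8 visit is not before it.
- **Section 13 already requires blinded central raters.** It does, so a breach would be a protocol deviation. A reader should therefore not infer that a Week 8 rating by an unblinded person must stay in the analysis. Section 13 does not say, however, what happens to PP status after a breach.
- **The list is open-ended, and protocol 16.1 describes PP in terms of adherence.** An exclusion could be made on that basis. But SAP 1.2 says the SAP replaces the protocol's analysis plan, and an open-ended list permits the exclusion without prespecifying it.

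**Conclusion.** The concern holds for Weeks 4 and 8. The one post-baseline rater check in the primary set names an instrument the protocol does not schedule then, and both HAM-D17 responses in the primary model have no explicit check of their rater. The protection that remains is partial. The bias that could follow cannot be sized, because the documents do not say how often a non-central rater might score the HAM-D17.

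Two stronger inferences are not supported. The first is that the primary set is empty. That is one literal reading, but the list is worded permissively, and the reading under which nobody is excluded is at least as natural. The second is that the sponsor plainly meant HAM-D17 wherever QIDS-C16 appears. A misnamed instrument is a likely explanation after enrollment, but at baseline inclusion criterion 4 gives the QIDS-C16 a possible role.

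The conclusion assumes that Figure 1 and the visit lists are the full schedule. If QIDS-C16 ratings are in fact collected at Weeks 4 and 8, item (c) has data to act on, but the HAM-D17 rater still goes unchecked.

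**What to change.** 1. In SAP 3.2.1, after-enrollment (c), require that the Week 4 and Week 8 HAM-D17 was completed by the blinded central rater described in protocol section 13.
2. In the same item, remove the QIDS-C16 condition, or state that an absent post-baseline QIDS-C16 does not exclude a subject.
3. Leave baseline (c) in place, adding the HAM-D17 by name if wished, until inclusion criterion 4 has been reconciled with Figure 1 and section 9.3 on whether a baseline QIDS-C16 is collected. Replacing the QIDS-C16 there first could delete the named rater check on a real eligibility score.

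The change should be made before evaluability is determined for the 8-week analysis. For the PP rule it costs SAP wording, and possibly a few more PP exclusions; the baseline reconciliation may also need protocol wording. The new check presupposes that the rater's role is recorded with each HAM-D17, as the present item already presupposes for the QIDS-C16.
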